## ***Protocol***

### ***Population***

We will enroll mothers aged  $\geq 18$  years who have a child 2 years old or younger and who are currently enrolled in WIC in North Carolina. Caregivers must have a smartphone (i.e., a cell phone that can send and receive text messages and access the internet), be willing to send and receive study-related text messages, have an email address they check regularly, have regular access to the internet, and be comfortable reading and writing in English.

### ***Recruitment***

The target enrollment is 50 participants in accordance with published guidance for pilot studies and to allow for drop-outs. We partnered with two different entities for participant recruitment, using different strategies. The first is a private, non-profit health system that operates Federally qualified community health centers in North Carolina that also administer WIC benefits. During WIC encounters, WIC nutritionists (n=2) will upload the name, phone number and email address of WIC beneficiaries who are interested in joining the pilot into a secure online Duke Box folder. Research assistants will upload this information into REDCap (Research Electronic Data Capture), a secure, web-based software platform designed to support data capture and management for research studies. The second recruitment entity is the WIC office from the 2nd most populated county in North Carolina. This county WIC office will include flyers in mailings sent to all new WIC recipients. These flyers will provide information about the pilot study and will include a QR code that caregivers can scan to take them directly to the screener.

Additionally, the Nutrition Services Branch within the North Carolina Division of Public Health, which implements the WIC program for North Carolina, will alert all WIC directors in the state of the pilot study via email. The email will include the flyer with the QR code for WIC directors to distribute throughout their WIC clinics as they see fit. We will also utilize social media platforms, such as Facebook, and Duke University websites to distribute information about the study and aid in recruitment. Interested caregivers can also find a link to the screener from a study-specific website, <https://healthyrootsstudy.com>. This website contains study and contact information for the research team.

### ***Screening, baseline assessments, and enrollment***

All study related processes will be completed electronically to aid in the dissemination potential. Surveys are administered through REDCap, allowing caregivers to self-guide themselves through each one. The system incorporates functions such as scheduling surveys and tracking completion. If surveys are not complete, the system will automatically send reminders, via SMS text message and email, for up to 7 days.

The first survey is the eligibility screener which includes questions regarding eligibility criteria, as described above. As soon as contact information is entered into REDCap by the research

assistant the system will automatically email a link to the online screener and send a SMS text the following day if not complete. Interested caregivers will also be able to access the screener by scanning the QR code on the flyer or clicking on the screener link found on the study website and Facebook page. If the caregiver is eligible, they will confirm their contact information and be directed to an online consent form (see Figure 2 for study flow). Once the consent form is electronically signed, caregivers will be directed to complete an online baseline survey.

Upon completion of the baseline survey, participants will be asked via email to complete two 24-hour dietary recall assessments administered through the Automated Self-Administered 24-Hour Dietary Assessment Tool (ASA24). The ASA24 is a freely available, web-based, self-administered tool developed by the National Cancer Institute and provides comprehensive nutrient data on all foods and beverages consumed during the previous 24-hour period. Caregivers will be asked to complete two separate 24-hour dietary recalls (1 week and 1 weekend day) within two weeks of each other. When both ASA24s are complete caregivers will be enrolled in the intervention.

Once the participant is enrolled, they will begin receiving SMS text messages. The first text message will include a web link to a study-specific YouTube channel that includes an orientation video. This 2-minute orientation video informs participants of what to expect including surveys they have to complete and incentives for completing those surveys. They are presented with the study schedule and contact information for the study team and encouraged to reach out with any questions or concerns. Subsequently, participants will receive their first goal, followed by a new goal every 2 weeks until the end of the study for a total of 6 goals. During each 2-week goal cycle, participants will receive 3 tips per week related to that goal. At the end of each week, they will receive a tracking message related to their assigned goal. If they respond, they will receive feedback on their progress. If they do not respond they will receive an automated reminder. If still no response, they will receive a reminder to track next time as well as a tip. After 12 weeks, participants will be asked to complete two more ASA24s and a satisfaction survey. Participants will receive a gift card after completion of each ASA24 (n=4) for a maximum amount of \$55.

#### ***Data collection and outcome assessments***

Self-reported sociodemographic characteristics, including education, age, BMI (kg/m^2), marital status, employment, depression, race, and ethnicity will be collected prior to enrollment through REDCap online surveys (Table 2). REDCap will also be used to capture intervention retention defined as responding to weekly tracking surveys. REDCap will also be used to capture post-intervention satisfaction survey. Research staff will follow up with phone calls and text messages for those who do not complete the satisfaction survey.

**Table 2:** Schedule of Assessments

| Measure               | Screening | Baseline | 12 weeks |
|------------------------------|------------------|-----------------|-----------------|
| Inclusion/exclusion criteria | X                |                 |                 |
| Informed consent             | X                |                 |                 |
| Sociodemographics            |                  | X               |                 |
| Food insecurity  |                  | X               |                 |
| WIC shopping habits          |                  | X               | X               |
| Depression       |                  | X               |                 |

|                                      |  |   |   |
|--------------------------------------|--|---|---|
| Everyday Discrimination  |  | X |   |
| ASA24 Dietary Tracking               |  | X | X |
| Satisfaction Survey                  |  |   | X |

2-item screen for food insecurity

Personal Health Questionnaire Depression Scale (PHQ-8)

Expanded Everyday Discrimination Scale

### ***Analytic Approach***

#### ***Primary Outcomes***

*Implementation* will be assessed through intervention engagement calculated by dividing the number of days with valid tracking data (numerator) over the total number of possible tracking days (denominator). We will calculate and compare engagement rates by week. We will create a dichotomous outcome variable comparing high vs. low engagers using an established cutoff of 80% or more engagement in weekly self-monitoring . Bivariate analyses using *t* tests and chi-square will be used to examine predictors of intervention engagement. Poisson regression with a robust variance will be used to examine sociodemographic differences among those with higher levels of engagement (80% or more weeks of tracking) and estimate risk ratios and 95% confidence intervals.

*Preliminary efficacy* will be measured by assessing changes in diet quality. Dietary intake will be measured using the ASA24 recall tool. Participants will be asked via email to complete 2 separate dietary recalls (1 week and 1 weekend day) within a 14-day period prior to enrollment and again upon study completion, for a total of 4 dietary recalls. These data will be used to calculate a Healthy Eating Index-2015 (HEI) score, which consists of 13 components, 9 of which assess adequacy of the diet, including 1) total fruit; 2) whole fruit; 3) total vegetables; 4) greens and beans (including peas); 5) whole grains; 6) dairy; 7) total protein foods; 8) seafood and plant proteins; and 9) fatty acids, which is a ratio of poly- and mono- unsaturated to saturated fatty acids. The remaining 4 assess dietary components recommended to be consumed in moderation: 10) refined grains; 11) sodium; 12) added sugars; and 13) saturated fats . For all components, higher scores reflect better diet quality as moderation components are reverse scored. Each component is scored on a density basis rather than absolute scores, either as a percentage of calories or per 1000 calories allowing use of the HEI for a range of ages and populations. Summed scores of the 13 components yield a maximum total score of 100, with a higher score reflecting greater compliance with the 2015–2020 Dietary Guidelines for Americans .

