#### ***Analysis***

Data from this pilot study will be descriptive with outcomes being estimates of variables relating to feasibility . Sample characteristics will be described as frequencies for categorical variables and means for continuous variables. HEI-2015 scores will be summarized as means and standard deviations and percent maximum score [(mean score/maximum score) x 100%]. We will explore intervention effects on change in HEI score from baseline to 12 weeks using a two-sample *t*-test. Although we will likely not have enough power, we will conduct exploratory analyses to assess differences in HEI scores among low vs. high engagers using linear regression. Similar analysis will be conducted for changes in relevant behavioral and psychosocial variables.

If the distribution of any outcome is heavily skewed, we will either appropriately transform the data so it's normally distributed or use a generalized linear mixed model with an appropriate link function. Sensitivity analyses will fit linear mixed models with a full maximum likelihood estimation using all available data to allow for responses to be missing at random, where the missing mechanism may be related to either observed covariates or response variables, but not related to the unobserved data. All analyses will be conducted using STATA 14 (StataCorp, College Station, TX).

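### Does a day-based engagement formula, with no stated rule for early leavers, leave the implementation primary outcome undefined?

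*SAP*

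**What the plan says.** The SAP (Primary Outcomes) computes engagement by "dividing the number of days with valid tracking data (numerator) over the total number of possible tracking days (denominator". The same paragraph then works in weeks. It announces "We will calculate and compare engagement rates by week", dichotomises at an "established cutoff of 80% or more engagement in weekly self-monitoring", and describes the high group in the Poisson model as "80% or more weeks of tracking".

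The Protocol (Screening, baseline assessments, and enrollment) gives the schedule: six goals, each lasting two weeks, and "At the end of each week, they will receive a tracking message related to their assigned goal". A participant who does not answer gets an automated reminder. If there is still no answer, a further message encourages tracking the next time. Under Data collection and outcome assessments the same weekly replies appear under another name: "REDCap will also be used to capture intervention retention defined as responding to weekly tracking surveys".

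On attrition, the Protocol (Recruitment) says "The target enrollment is 50 participants in accordance with published guidance for pilot studies and to allow for drop-outs", without a rate. The SAP's only missing-data text (Analysis) is "Sensitivity analyses will fit linear mixed models with a full maximum likelihood estimation using all available data".

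**The concern.** Three things look wrong.

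- **Unit.** The formula counts days, but nothing in either document describes daily tracking, and the cutoff beside it is in weeks.
- **Denominator.** Possible occasions could mean all 12 prompts, or only those sent before a participant left. Drop-outs are expected, and the mixed-model provision deals with missing responses. It does not define a ratio in which not responding is itself the outcome.
- **Terms.** A valid response is not defined, and the protocol calls the same weekly replies retention.

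Engagement is a primary outcome. It supplies the weekly rates, the high/low split, the bivariate comparisons and the Poisson risk ratios. If two analysts could properly put the same early leaver in opposite groups, the main feasibility estimate would not be reproducible.

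**Working it through.** **Inputs.** From the Protocol: 6 goals, 2 weeks per goal, one tracking message per week, target enrolment 50. From the SAP: the 80% cutoff. The documents give no drop-out rate and no engagement figure to reproduce.

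**Unit**

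- Prompts: 6 × 2 × 1 = 12. Calendar days: 12 × 7 = 84.
- Calendar-day reading: one reply per week gives at most 12/84 = 14.3%. The cutoff would need 0.80 × 84 = 67.2, so 68 days. The high group would be empty by construction.
- Prompt reading: 0.80 × 12 = 9.6, so at least 10 prompts. 10/12 = 83.3% passes and 9/12 = 75.0% fails.

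Only the prompt reading gives a usable split, and it agrees with both weekly phrases in the SAP. Replacing days by weeks would change no result.

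**Early leavers, individual score.** Suppose a participant answers every prompt and leaves after week k.

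| k | Fixed: k/12 | Time in study: k/k |
|---|---|---|
| 2 | 16.7% (low) | 100% (high) |
| 6 | 50.0% (low) | 100% (high) |
| 9 | 75.0% (low) | 100% (high) |

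A leaver at or before week 9 is always low on the fixed denominator. Someone leaving after week 10 with 10 replies is high on both (10/12 = 83.3%; 10/10 = 100%). With 8 replies the two readings still part: 8/12 = 66.7% against 8/10 = 80%.

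**Early leavers, share of high engagers.** With d leavers by week 9 out of 50, the two readings differ by at most d/50:

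- d = 5: 5/50 = 10 points
- d = 10: 10/50 = 20 points
- d = 15: 15/50 = 30 points

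The minimum is 0 in each case, when no leaver reached 80% of their own weeks. As an upper-bound example, take d = 10, all leavers high before leaving, and 20 of 40 completers high. The share is 20/50 = 40% on the fixed denominator and (20 + 10)/50 = 60% on time in study. Each d, and the completer share, is assumed.

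**Rate in a single week.** If 40 remained at week 12 and 28 replied (both assumed), the rate is 28/50 = 56% of those enrolled or 28/40 = 70% of those remaining.

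**Which reading the text supports**

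- The formula divides by the total possible, which most naturally means the full schedule.
- The protocol's response to silence is to send more messages, and goals keep coming every two weeks. A participant who merely stops replying is still prompted and reaches a denominator of 12 on either reading.
- The readings part only for someone whose messages are stopped. The documents describe no such procedure and give no count.

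**Reach.** A participant who stays 12 weeks has a denominator of 12 either way. An early leaver would usually have no 12-week dietary recalls, hence no HEI change, and so would not enter the main exploratory comparison of HEI change by engagement. A mixed model on all available data could still include that person's baseline. The engagement rates and the predictor analyses remain exposed, to the extent shown above.

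**The case for a change.** The strongest case for a change is that this is a primary outcome of a pilot whose product is feasibility estimates. A denominator that can be settled after the data are seen weakens such an estimate. The SAP never says that possible days are the 12 prompts, and its formula already cannot be taken literally in calendar days. Because the protocol defines retention through the same replies, leaving is not separated from falling silent. It is also open whether a reply after the automated reminder counts for that week. One sentence would settle all this without new data.

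Some of this stands. The wording is loose, a valid response is undefined, and no explicit rule covers people taken off messaging. But the sentence asked for would restate the reading that the plan already supports, so it would leave the result as it is. The larger shifts need leavers who tracked at or above 80% and were then removed from prompts, and no figure in the documents points to that. Two names for the weekly replies cause no error in the analysis. Renaming retention would remove the protocol's only definition of it. Finally, the SAP calls the pilot descriptive, and neither document ties a progression decision to the engagement rate.

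**Conclusion.** The inconsistency in wording is real, but no change to the plan is needed. Read with the protocol's schedule, engagement is weeks tracked out of 12 and high engagement is at least 10 of 12. The day/week slip has no numerical effect on that reading. The missing rule for leavers is a gap that analysts can fill sensibly from the full schedule, and a report that states its denominator would let a reader see that they had.

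The residual uncertainty in the share of high engagers runs from 0 up to 10, 20 or 30 percentage points for an assumed 5, 10 or 15 leavers by week 9 out of 50. The upper ends require that every leaver's messages were stopped and that every one had met 80% until then. The conclusion rests on two readings of the text: one tracking occasion per week, and prompts that continue when a participant goes silent. If daily tracking were in fact collected, or messages routinely stopped after non-response, the point would need another look. Neither document says so.

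### The only regression for predictors of engagement uses a high/low split at 80%, which loses information in a 50-person pilot; a model of weeks tracked should be added beside it

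*SAP*

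**What the plan says.** The Protocol (Screening, baseline assessments, and enrollment) describes weekly tracking: "At the end of each week, they will receive a tracking message related to their assigned goal". Participants receive "a new goal every 2 weeks until the end of the study for a total of 6 goals", and the follow-up assessments come after 12 weeks.

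The SAP (Primary Outcomes) handles engagement in four steps:
- It defines engagement as a proportion, counted in days tracked over possible tracking days.
- It adds: "We will calculate and compare engagement rates by week". No predictors are named for this comparison.
- It creates the split: "We will create a dichotomous outcome variable comparing high vs. low engagers using an established cutoff of 80% or more engagement in weekly self-monitoring".
- It looks for predictors in two ways. Bivariate *t* "tests and chi-square will be used to examine predictors of intervention engagement", with no statement of whether the outcome is the proportion or the split. A robust-variance Poisson regression then estimates risk ratios with 95% confidence intervals for reaching 80% or more of weeks.

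On sample size, the Protocol (Recruitment) says: "The target enrollment is 50 participants in accordance with published guidance for pilot studies and to allow for drop-outs". The SAP (Analysis) calls the pilot data descriptive. It concedes low power only for comparing diet scores between low and high engagers.

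**The concern.** Each participant can supply 12 weekly responses, and the regression reduces them to one yes/no value. The difference between 9 and 10 weeks counts in full; the difference between 0 and 9 weeks, or between 10 and 12, counts for nothing. Citing the cutoff as established is a good reason to report the share of participants who reach it. It is a weaker reason to make it the sole outcome of the predictor regression, when the sample is small and the finer data are collected anyway. At stake is the precision with which the pilot can describe who engages and who does not.

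**Working it through.** **Inputs from the documents.** Six goals × 2 weeks = 12 weekly prompts. Target N = 50. Cutoff 80%. Confidence level 95%. The plan gives no power figure, expected engagement rate or within-person correlation, so there is no stated result to reproduce.

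**Inputs assumed.** One binary predictor splitting the sample 25/25; two-sided 5% tests; beta-binomial weeks tracked; group means from 40% vs 60% to 65% vs 85%; within-person correlation 0.2 to 0.5. The unit is weeks, as in the SAP's regression sentence, although its definition of engagement counts days.

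**Step 1: the cutoff in whole weeks.** 0.8 × 12 = 9.6, so high means at least 10 of 12 (83.3%). Nine of 12 (75%) is low, as is 0 of 12.

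**Step 2: textbook benchmark.** If engagement were normally distributed, splitting it so that a share *p* is high keeps φ(c)² / [p(1 − p)] of the information, where c is the normal quantile at 1 − p.
- p = 0.5: 0.399² / 0.25 = 0.64, an effective N of about 50 × 0.64 = 32.
- p = 0.2 or 0.8: 0.280² / 0.16 = 0.49, an effective N of about 50 × 0.49 = 25.

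Weeks out of 12 are bounded and probably not normal, so this is only a guide.

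**Step 3: simulation on the 12-week scale (20,000 runs per case).** Three tests were compared:
- *Weeks model*: fractional logit of weeks/12 with robust standard error.
- *Planned regression*: Wald test of ln(pA/pB), with SE = √[(1 − pA)/(25 pA) + (1 − pB)/(25 pB)], where pA and pB are the shares with 10 or more weeks. With a single binary predictor this is what robust Poisson gives, apart from a small-sample factor.
- *Chi-square* on the same split.

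Power, in %:

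| Mean tracking | Correlation | Weeks model | Wald | Chi-square | Gap to Wald | Gap to chi-square |
|---|---|---|---|---|---|---|
| 40 vs 60 | 0.2 | 77 | 18 | 45 | 59 | 32 |
| 55 vs 75 | 0.2 | 81 | 57 | 66 | 24 | 15 |
| 55 vs 75 | 0.35 | 63 | 45 | 56 | 18 | 7 |
| 55 vs 75 | 0.5 | 50 | 37 | 48 | 13 | 2 |
| 65 vs 85 | 0.5 | 58 | 50 | 57 | 8 | 1 |

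The first and last rows are the extremes of the range. Simulation error is at most √(0.25/20,000) = 0.35 points per power figure.

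**Step 4: what drives the gap.** With no true difference, the rejection rate was about 4.8% for the weeks model, 3.4% for the Wald test and 6% for chi-square. The Wald test is therefore conservative, and that accounts for part of its shortfall. Chi-square is slightly liberal and flatters the split a little. The loss due to the split itself is better judged from the chi-square column, and is probably somewhat more than that column shows.

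The 59-point case has a further cause. Only about 8% of the lower group are high engagers, so that group has none at all in about 0.92²⁵ = 12% of samples. The risk ratio then cannot be estimated, and the run was counted as not significant.

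**Step 5: pattern.** The loss is large when most participants fall below 80% or engagement is widely spread. It is small when engagement is high and people track either nearly always or rarely. Extending the correlation to 0.6, the split kept between 42% and 92% of the information.

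**The case against.** A reader might infer that every predictor analysis uses the split. The SAP does not say so. Pairing *t* tests with chi-square most naturally means comparing high with low engagers. But engagement was first defined as a proportion, and a *t* test of that proportion between, say, married and unmarried mothers fits the wording. Weekly rates are analysed as well, though not by predictor. What stands is that the only regression is on the split and that the bivariate scale is unstated.

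A reader might also infer that the loss is large whatever happens. The documents give no engagement distribution, and at 65% vs 85% with correlation 0.5 the split costs almost nothing against chi-square.

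Nor do the documents make identifying predictors a primary aim. The primary outcome is implementation, measured by engagement; the predictor work follows from it in a pilot described as descriptive, with N taken from pilot guidance rather than power. Even the weeks model reaches only 50% to 63% power in the middle case at the two higher correlations, so neither analysis would identify predictors reliably. This limits the importance of the point. It does not remove it, because the SAP does specify tests and interval estimates, and their precision matters.

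Finally, a risk ratio for reaching a cited adherence threshold is a legitimate target, and replacing it would change the question. That objection holds, and it is why the weeks model belongs beside the 80% analysis and not in its place.

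**Conclusion.** The point holds in a limited form. The plan's only predictor regression discards the difference between 0 and 9 weeks of tracking, and the scale of its bivariate tests is undefined. Over the assumed range, modelling weeks tracked gains about 8 to 59 points of power over the planned Wald test and about 1 to 32 points over chi-square on the same split. These figures rest on a 25/25 binary predictor, beta-binomial weeks, all 50 participants analysed, and engagement levels and correlations that the documents do not supply. The direction is consistent across the scenarios; the size is not known in advance. It is an improvement worth making to an exploratory analysis, and it casts no doubt on the 80% share as a feasibility measure or on the pilot as a whole.

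**What to change.** - Keep the share of participants at or above 80% as a feasibility figure, and give its 95% confidence interval. Keep the robust Poisson risk-ratio model.
- Add a predictor model of weeks tracked out of 12: a fractional or quasi-binomial logit with robust standard errors. Alternatively, fit a logistic GEE to the weekly responses, clustered by participant. With week as a covariate, the GEE also supports the planned by-week comparison, but it is then not strictly the same model as the fractional logit, so the SAP should name one in advance.
- Run the bivariate tests on the proportion of weeks tracked, and label any chi-square test on the 80% variable as such.
- Reconcile days with weeks in the definition of engagement, so that numerator and denominator match the weekly prompts.

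The cost is some SAP wording and one extra model on data already collected. The downside is that an odds ratio or mean difference is reported beside the risk ratio, and readers need to be told why both appear.
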